By my signature below, I agree to conduct this Study in accordance with the Clinical Trial Protocol, current Good Clinical Practice (cGCP) and Good Laboratory Practice (cGLP) guidelines, obligations as set forth in Title 21 CFR Parts 812, 54, 56 and 11 (as applicable), and any applicable regulatory laws. I will make no changes to protocol-defined procedures without written permission from the Sponsor.

I understand that Investigational Use Products may be used **only** for the purposes explicitly described in this protocol.

I further agree to treat the results of this Study as confidential information and will not submit the results of the Study for publication without prior written authorization from the Sponsor.

[name]

02/19/2021

PRINTED NAME

SIGNATURE

DATE

SYNOPSIS

Title of Study	Study evaluating efficacy of a non-invasive pelvic floor muscle trainer for treatment of stress urinary incontinence.
Objectives	Evaluate efficacy of Pelex Upp in treatment of patients with stress urinary incontinence.
Planned Number of Subjects and Duration of Involvement	5 study subjects will be enrolled for a total of 4 weeks.
Patient Population	Women > 18 years of age with symptoms of stress urinary incontinence
Investigational Product Name	Pelex Upp
Methodology Overview	
This will be a prospective cohort study of women > 18 years of age with symptoms of stress urinary incontinence, recruited via an online recruitment tool.
 
After screening, patients meeting inclusion criteria will be given a study brochure, and then given instructions on how to indicate desire to participate in the study. The patient will then be contacted for study participation, including explanation of study and details and completion of Informed Consent. Participants will then complete a pre-treatment urinary incontinence symptom questionnaire(ICIQ).
 
After completion of the above, the participants will then be given a Pelex Upp study, in addition to educational materials on use of the device, and a treatment schedule. Participants will perform a standardized biofeedback-mediated pelvic floor muscle training program with the study device 10 minutes a day, five times a week for 4 weeks. There will be a mid-study check in to assure all devices are functioning appropriately. At the end of the study, participants will complete a post-treatment urinary incontinence symptom questionnaire(ICIQ).
 
Endpoint of the study will be change in stress urinary incontinence symptoms as measured by the ICIQ. The ICIQ will be collected at 2 time points: before study entry, and at study close.

ABBREVIATIONS

PFMT	Pelvic floor muscle training
SUI	Stress urinary incontinence
OAB	Overactive bladder
UI	Urinary incontinence
PFM	Pelvic floor muscles
US/USA	United States of America

TABLE OF CONTENTS

1	INTRODUCTION	11
2	DESCRIPTION OF THE INVESTIGATIONAL PRODUCT	11
2.1	Overview	11
2.2	Proposed Intended Use Statement	11
3	STUDY OBJECTIVES	11
4	STUDY OVERVIEW	12
4.1	Study Approach	12
4.3	Study Duration.....	13
5	STUDY POPULATION	14
5.1	Sample Size and Target Study Population	14
5.1.1	Sample size	14
5.1.2	Study population	14
5.1.3	Alignment with intended study population.....	14
5.1.4	Alignment with intended use of the device.....	14
5.2	Recruitment Methods	14
5.2.1	Recruitment for Study	14
5.2.2	Duration of study activities.....	14
5.3	Patient Selection	15
6	STUDY MATERIALS	15
6.1	Investigational Product.....	15
6.1.1	Identity of the investigational product and accessories	15
6.1.2	Safety issues.....	16
6.1.3	Handling, storage, accountability.....	16
6.1.4	Required training.....	16
6.1.5	External studies.....	17
6.2	Other Study Materials	17
6.2.1	Materials to be provided by study site.....	17

1 INTRODUCTION

Pelex, Inc. is a medical device company that is dedicated to addressing pelvic health disorders. The company is developing a non-invasive medical device that uses electromyography and neurostimulation to treat incontinence and other pelvic floor disorders. In support of its research and development efforts, Pelex is conducting a clinical study to assess the efficacy and usability of the electromyography component of the company's pelvic health product. Five patients suffering from stress urinary incontinence, a form of pelvic floor disorder, will be recruited to participate and the duration of participation is expected to be four weeks. The result of this study will be used to verify that the underlying technology functions as expected, identify subject preferences for device form factor and other design decisions, and capture other patient feedback.

2 DESCRIPTION OF THE INVESTIGATIONAL PRODUCT

2.1 Overview

The Pelex Upp is a non-invasive device that is designed to guide a user through personalized pelvic floor strengthening exercises. The device consists of a patient contact interface approximately 12" x 6" whose upper surface is embedded with disposable electrodes which by a short cable is linked to an enclosed circuit board component. When a patient interacts with the patient contact interface by sitting upon it, the electrodes of the sensor array are able to detect and measure the patient's muscle contractions. The circuit board component analyzes the collected data and provides feedback to the patient on sensor array placement and strength of muscle contractions via a user interface panel consisting of LEDs that is located on a handheld piece that is connected to the hardware component by a fixed cable. The handheld component also houses a cadence LED, which prompts the user through a series of standardized pelvic floor contraction and relaxation exercises.

2.2 Proposed Intended Use Statement

The Pelex Upp is a non-invasive electromyography device designed to treat stress urinary incontinence in adults.

3 STUDY OBJECTIVES

The principal objective of this study is to demonstrate efficacy of the Pelex Upp in treatment of stress urinary incontinence. The secondary objective will be to determine ease of use of the Pelex Upp by patients at home.

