7 STUDY PROCEDURES

7.1 Workflow

The study design is a prospective cohort that enrolls adult female patients identified as having stress urinary incontinence via an online enrollment form to evaluate the effectiveness of the Pelex Upp in treatment of stress urinary incontinence. The treatment group will enroll 5 subjects. Following the granting of Informed Consent, subjects will be enrolled in the study within the prospective cohort and will complete a four-week course of biofeedback augmented PFMT using the Pelex Upp. Patients will complete a pre- and post-study urinary incontinence quality of life evaluation tool to assess response to the investigational device.

Subsequent treatment and work up will be dictated by the reported persistence of symptoms. Follow-up with care providers will be as needed, as determined by the patient.

[figure not shown]

Figure 1: Study Workflow

Item
1. Study Brochure
2. Prospective Subject Screening Questionnaire
3. Subject Consent Form
4. Instructional Materials
5. Study Package with Study Materials
6. Pre-Study Questionnaire
7. Post-Use Questionnaire
8. Study Initiation Check-in Communication
9. Mid-Study Check-in Communication
10. Post-Study Questionnaire
11. Thank You Communication

Table 1: Study Materials

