7.3 Randomization and Blinding

No randomization nor blinding will occur.

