9 STATISTICAL METHODS

9.1 Determination of Sample Size

This study is exploratory and not designed to establish non-inferiority or superiority. Therefore, determining a sample size for the purposes of statistical significance is not necessary.

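### Section 3 sets out to demonstrate efficacy, but Section 9.1 calls the study exploratory, and an uncontrolled before-after study of about 5 women can only estimate within-participant change

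*Protocol*

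**What the plan says.** Section 3 (Study Objectives): "The principal objective of this study is to demonstrate efficacy of the Pelex Upp in treatment of stress urinary incontinence". Ease of use at home is the secondary objective.

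Section 9.1 (Determination of Sample Size): "This study is exploratory and not designed to establish non-inferiority or superiority". The same section gives this as the reason why no sample-size calculation is needed.

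Other statements of purpose are milder:

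- Synopsis, Objectives: "Evaluate efficacy of Pelex Upp in treatment of patients with stress urinary incontinence".
- Section 7.1: "to evaluate the effectiveness of the Pelex Upp in treatment of stress urinary incontinence".
- Section 1: "to assess the efficacy and usability of the electromyography component". It then lists the uses of the result: checking that the technology works as expected, learning preferences on form factor and design, and collecting feedback.
- Sections 4.1 and 5.1.1 speak of *determining* efficacy, in each case while calling the study a pilot.
- Section 11.2 expects confirmation of clinical efficacy to come from later studies that these data make possible.

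On design, Section 7.1 says "The treatment group will enroll 5 subjects" and Section 7.3 says "No randomization nor blinding will occur". In the synopsis the endpoint is change in symptoms on the ICIQ: "The ICIQ will be collected at 2 time points: before study entry, and at study close". Section 9.3 adds two contraction measures at entry and exit. Section 5.1.3 mentions that other patients might serve as controls, but no section defines a control group, its size, its procedures or a comparison with it.

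**The concern.** The principal objective frames what the final report may conclude, and Section 12.7 allows for journal submission. As written, Section 3 invites the conclusion that efficacy was shown if ICIQ scores improve. Section 9.1 disclaims that kind of conclusion and relies on the disclaimer to go without a sample-size justification. The protocol cannot be exploratory when the number of participants is set and demonstrative when the objective is stated.

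The objective is fixed in the protocol itself. It is not a detail left to a statistical analysis plan, which would take the objective over as it stands.

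**Working it through.** **1. The statements of purpose side by side**

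| Place | Verb or role | Consistent with Section 9.1? |
|---|---|---|
| Synopsis, Objectives | evaluate | yes |
| Section 1 | assess; uses are technical checks and feedback | yes |
| Section 7.1 | evaluate | yes |
| Sections 4.1, 5.1.1 | determine, within a pilot | loosely; align for consistency |
| Section 11.2 | confirmation comes from later studies | yes |
| Section 3 | demonstrate | no |

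Section 3 is the statement in open conflict with Section 9.1.

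**2. What the design can identify**

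Write the expected change in ICIQ as

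expected change = P + B,

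where P is the effect of the device-guided programme and B collects change over time, regression to the mean, expectation, and the effect of answering the questionnaire twice. Regression to the mean is relevant because women are enrolled for having symptoms, and Table 1 in Section 5.3 establishes those symptoms with the ICIQ, which is also the endpoint. Expectation is relevant because the outcome is self-reported without blinding.

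One group measured twice yields one quantity, P + B. A larger n shrinks the standard error of that sum (SD/√n) but leaves B unchanged. Without a comparison group P is therefore not identified, whether n is 5 or 500.

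**3. Precision, as illustration only**

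The only input from the protocol is n = 5 (Section 7.1 and synopsis). It states no test, confidence level, SD or responder definition, so there is no planned figure to reproduce. The assumptions here are a two-sided 95% level, a t-interval for mean change, independent participants and, for the second line, a yes/no classification of improvement.

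- Half-width of the interval for mean change, in SDs of the change, is t(0.975, n−1)/√n. For n = 5: 2.776/2.236 = 1.24. For 4 completers: 3.182/2 = 1.59.
- Exact (Clopper-Pearson) lower limit when all n improve is 0.025^(1/n). For 5 of 5: 0.025^(1/5) = 0.478, so 48% to 100%. For 4 of 4: 0.025^(1/4) = 0.398, so 40% to 100%.

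These figures describe how imprecise the estimate would be. Step 2 would stand without them.

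**The case against.** The strongest reply is that the protocol read as a whole does not set up a confirmatory claim. Section 1 limits the use of the result, Section 11.2 defers confirmation, Sections 4.1 and 5.1.1 call the study a pilot, and Section 9.1 disclaims superiority and non-inferiority. No text forces a demonstrated or not-demonstrated verdict. All of this stands. It limits the point to the wording of the objective and to what may be concluded, and it also shows that the wording of Section 3 does not belong.

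A second reply is that replacing *demonstrate* with the synopsis verb *evaluate* would be enough. That would remove the textual conflict. It would not say what quantity is being evaluated, nor stop a before-after change from being reported as efficacy shown.

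Three stronger readings are tempting, and the protocol does not support them.

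- *The study cannot separate the device from the exercises.* Section 2.1 describes a device that guides the exercises, and the synopsis and Section 7.1 define the treatment as biofeedback-supported training with it. Guided exercise is part of the intervention, and no objective asks for a gain over exercise alone.
- *The result must be read against the 84% success rate in Section 4.1.* That figure is an upper value in selected patients, with success undefined, and the protocol claims no superiority to pelvic floor training. It has no bearing here.
- *Five women are too few.* A pilot of 5 is not wrong in itself, and sample size is not the main barrier. With a two-sided 5% paired t-test, again an assumption, a mean change of about 1.68 SD would be detected with 80% power at n = 5. It would still be only a before-after change.

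**Conclusion.** The point holds as a mismatch between the principal objective and both the declared status and the design of the study. Section 3 promises a demonstration of efficacy. Section 9.1 disclaims one, and a single unblinded group without a defined comparator cannot provide one at any sample size. What the study can give is an imprecise estimate of four-week within-participant change, together with information on ease of use.

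The conclusion rests on the protocol's own text and on the absence of a defined comparison. It does not depend on the illustrative 1.24 SD half-width or the 48% to 100% interval, which use assumptions that the protocol does not state. The correction should be made because it governs what may be concluded. Conduct, data and planned analyses are unaffected.

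**What to change.** 1. In Section 3, replace the aim of demonstrating efficacy with exploratory wording that agrees with the synopsis, for example: to evaluate, in an exploratory manner, the four-week within-participant change in ICIQ during use of the Pelex Upp. Keep the contraction measures of Section 9.3 and the ease-of-use objective as they are.
2. Add to Section 9.1 that no confirmatory efficacy conclusion will be drawn from this uncontrolled before-after study.
3. For consistency, align the references to determining efficacy in Sections 4.1 and 5.1.1, and reconcile the undeveloped sentence on possible controls in Section 5.1.3 with the single-group design.

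No participants, procedures or analyses are added. The cost is a more modest stated claim and a protocol revision that goes through IRB review (Section 13.3).

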4 STUDY OVERVIEW

4.1 Study Approach

Urinary incontinence (UI), as defined by the International Continence Society as any involuntary loss of urine, is among the most prevalent of all medical conditions, affecting one in four adult women and increasing in incidence with age (1). Stress urinary incontinence (SUI), which is the involuntary loss of urine during exertion, sneezing or coughing, is the most common form of UI (2) and is estimated to be responsible for over \$12 Billion in health care expenditures annually (3). SUI is typically the result of weakening of the pelvic floor muscles and atrophy of vaginal tissues, both of which occur increasingly with age and after childbirth(4).

Therapies for SUI primarily revolve around restoring the strength and function of the pelvic floor muscles (PFM), and can be understood as lying on a spectrum between more conservative and more invasive options. First line (conservative) therapy for SUI typically consists of behavioral modification, such as more frequent urinating to avoid larger bladder volumes, in addition to some form of pelvic floor muscle training (PFMT)(2), while more invasive options, such as surgery to reconstruct the pelvic floor, are reserved for patients who have failed first line therapy.

The goal of PFMT is to increase the strength, coordination and endurance of PFM, which allows for stabilization of the urethra and pelvic organs during rises in intra-abdominal pressure(5), thereby avoiding loss of urine during these pressure rises. PFMT in the form of Kegel exercises is a well-established form of treatment for urinary incontinence (6), and success rates with PFMT for UI approach 84% in selected patients (7; 8), which, combined with their relative simplicity, make them a highly desirable and often-used treatment option. Most simply, PFMT is performed in the form of daily timed contractions and relaxations of the pelvic floor, typically after being coached about appropriate muscle use by a trained professional during a clinic visit (9). While this has been proven to improve SUI symptoms over behavioral therapy alone, PFMT with biofeedback, where a device is used to record the biological signal of contraction of the PFM and then present that signal to the user in audio or visual form, has been proven to offer even greater benefit than PFMT alone(10). Biofeedback in the setting of PFMT is accomplished by placement of surface electrodes on the skin overlying the pelvic floor muscles, or an intravaginal device sensitive to pressure changes, both of which can detect contraction and relaxation of the pelvic floor muscles and allows the user to then gain greater awareness of their PFM. Patients undergoing PFMT plus biofeedback typically do so under the guidance of weekly visits to a physical therapist, usually over the course of four to six weeks.

There is a robust body of evidence supporting use of biofeedback during PFMT in the treatment of all forms of urinary incontinence. In a systematic review in 2011, Herdershee et al(10) evaluated all randomized controlled trials (RCT) that compared PFMT alone to PFMT plus various types of feedback, including biofeedback, in treatment of urinary incontinence in women, and found across all studies, patients treated with PFMT plus biofeedback were significantly more likely to report improvement or resolution of their urinary incontinence,

though the authors pointed out that the results also could be partially attributable to more contact with health care providers (10). In another recent analysis, Glazer et al (11), using more inclusive inclusion criteria, also found a general benefit to biofeedback for treatment of urinary incontinence when compared not only to PFMT alone, but also medications and electrical stimulation. However, a more recent meta-analysis was more equivocal in its findings, with significantly better objective results, such as pad tests, in patients undergoing PFMT plus biofeedback, but with not as clear a difference in subjective quality of life (QoL) measures as compared to PFMT alone (12).

While PFMT plus biofeedback has traditionally been performed in a medical facility, whether it be a clinician's office or physical therapist's, more recent research has looked to leverage the ability to perform biofeedback at home to improve outcomes. This movement has been aided by the development in recent years of several medical devices designed to help patients perform biofeedback for PFM exercises at home, and thus avoid the need for recurrent trips to the physical therapist or physician's office. In a recent study, use of a home biofeedback device was found to be as efficacious as a standard twelve week PFMT program with four weekly visits to a physical therapist in treating women with predominantly SUI symptoms (13). In pilot studies, other devices have also shown promising rates of improvement in urinary incontinence when used at home and without other PFMT training (14). The use of medical devices to perform biofeedback at home is not only much more convenient than typical PFMT plus biofeedback, it has the potential to increase access to treatment overall. In a study by Washington et al, over one third of patients referred to a physical therapist for PFMT did not ultimately undergo treatment, with lack of insurance being the variable most associated with non-participation in treatment (15). Considering that the out-of-pocket cost of an initial physical therapist visit for PFMT is \$500 (15), while most of the devices designed for home biofeedback use are priced several hundred dollars less (13), these devices could greatly expand treatment capability.

However, despite the advantages these devices provide, there are still significant barriers to use. Due to the way biofeedback in conjunction with PFMT must be performed, specifically capture of the contraction and relaxation of the PFM, devices designed for use in these setting are either invasive (inserted into the vagina or rectum) or require placement by a trained professional (surface EMG electrodes). This presents a barrier to use for patients, and an opportunity for innovation. Specifically, the product under investigation, the Pelex Upp is designed for use at home for biofeedback plus PFMT sessions. It has a non-invasive patient interface that takes advantage of the unique anatomical properties of the perineum, the skin between the anus and vagina or scrotum, allowing the patient to perform PFMT plus biofeedback without the need for invasive devices or professionally placed electrodes.

The aim of the present pilot study is to determine efficacy of our product in the treatment of SUI in a home setting. Since PFMT plus biofeedback is considered standard of care in patients with SUI who are therapy-naïve, the study subjects will be exposed to no greater than normal risk associated with treatment. Study subjects will undergo evaluation by a treating physician and will have prescribed a treatment regimen typical for the disease process.

4.3 Study Duration

The study will last approximately a total of four weeks.

5 STUDY POPULATION

5.1 Sample Size and Target Study Population

5.1.1 Sample size

The total number of individual subjects is expected to reach approximately 5. This estimate is based on this being a pilot study, with the primary goal of determining efficacy of the Pelex Upp in treatment of stress urinary incontinence in adult women.

5.1.2 Study population

The study population will be representative of adults at least 18 years of age with symptoms of stress urinary incontinence. It is anticipated that Pelex will enroll approximately 5 qualifying adults in total.

5.1.3 Alignment with intended study population

The study population includes patients likely to benefit from pelvic floor muscle training plus biofeedback. It may also include other patients who may provide controls.

5.1.4 Alignment with intended use of the device

The device under investigation is intended as a biofeedback device to be used during PFMT.

5.2 Recruitment Methods

5.2.1 Recruitment for Study

Eligible patients will be invited to participate in the study on a first-come, first-serve basis, subject to Pelex weekly recruitment goals. They will be informed of the possible risks of the procedure and will be required to give informed consent before study-specific procedures can proceed. A minimal financial inducement will not be offered, and subject recruitment materials will be used. Each subject will be informed that no personally relevant clinical information will be derived from the collected data, and that the only possible benefit to the subject is the improvement in their stress urinary incontinence. Medications will be documented. Each subject's involvement in the study will be limited to the period between signing of the informed consent form (ICF) and the end of the study, which is expected to be four weeks after study initiation.

